In the morning of Day 5, after pre-IP use assessments, the subjects will be administered a single pouch/single cigarette of the IP in the sequence to which they have been randomised. IP will be used for 20 minutes with standard use instructions. The cigarette will be smoked in approximately 5 minutes with puffs taken at regular intervals approximately 30 seconds apart. PK sampling will be done pre-IP use and at 2, 5, 7, 15, 20, 30, 45, 60, 90 minutes, 2, 4, 6 and 8 hours post-IP use start. Sampling for plasma cotinine levels will be taken pre-IP use and at 4 and 8 hours post-IP use start. Used pouches will be collected for analysis of nicotine extraction. Questionnaires will be administered to the subject at defined intervals throughout the day. Safety will be followed throughout the day. Subjects will leave the research clinic after completing all 8 h-assessments on Day 5.

Visit 3 (End-of-Study phone call)

A follow-up telephone call (Visit 3, end-of-study) will be made on Day 7 (± 1) to follow-up on adverse events.

Investigational Product (IP), dosage and mode of administration

- A: ZoneX #2, oral nicotine delivery product (OND), white tobacco-free nicotine pouch, 5.8 mg nicotine/pouch
- B: ZoneX #3, OND, white tobacco-free nicotine pouch, 10.1 mg nicotine/pouch
- C: Skruf snus fresh slim white, 10.9 mg nicotine/pouch
- D: [REDACTED]
- E: Marlboro Gold, conventional cigarette, 0.8 mg nicotine/cigarette

Duration of IP use

Single 20-minute use of each of the 4 oral nicotine products or a single cigarette use, followed by *ad lib* use of the product assigned that day until 10pm.

Duration of each subject's involvement in the study

Subjects will participate in the study for up to 35 days, including an up to 28-day screening period.

Pharmacokinetic (PK) assessments

Blood sampling for nicotine and cotinine plasma concentration analysis

Safety assessments

AEs

Clinical laboratory profile

Vital signs (blood pressure and pulse)

ECG

Subjective measures

PES, MCEQ, PPS

Statistical methods

No formal sample size calculation has been performed for this study. The proposed sample size is considered sufficient to provide adequate information for the study objectives.

Continuous data will be presented in terms of evaluable and missing observations, arithmetic mean, SD, median, minimum and maximum value. In addition, for the parameters AUC and C_{max} the geometric mean and geometric coefficient of variation (CV) will be presented.

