In the morning of Day 1, after pre-use assessments and confirmation of eligibility, the subjects will be randomised and then administered a single pouch/single cigarette of the IP in the sequence to which they have been randomised. Oral nicotine IP will be used for 20 minutes with standard use instructions. The cigarette will be smoked in approximately 5 minutes with puffs taken at regular intervals approximately 30 seconds apart. PK sampling will be done pre-IP use and at 2, 5, 7, 15, 20, 30, 45, 60, 90 minutes, 2, 4, 6 and 8 hours post-IP use start. Sampling for plasma cotinine levels will be taken pre-IP use and at 4, 8 and 12 hours post-IP use start. Used pouches will be collected for analysis of nicotine extraction. Questionnaires will be administered to the subject at defined intervals throughout the day. Safety will be followed throughout the day. Subjects will be allowed to use the IP, to which they are assigned that day, *ad lib* after the 8-hour timepoint until 10 pm.

In the morning of Day 2, after pre-IP use assessments, the subjects will be administered a single pouch/single cigarette of the IP in the sequence to which they have been randomised. IP will be used for 20 minutes with standard use instructions. The cigarette will be smoked in approximately 5 minutes with puffs taken at regular intervals approximately 30 seconds apart. PK sampling will be done pre-IP use and at 2, 5, 7, 15, 20, 30, 45, 60, 90 minutes, 2, 4, 6 and 8 hours post-IP use start. Sampling for plasma cotinine levels will be taken pre-IP use and at 4, 8 and 12 hours post-IP use start. Used pouches will be collected for analysis of nicotine extraction. Questionnaires will be administered to the subject at defined intervals throughout the day. Safety will be followed throughout the day. Subjects will be allowed to use the IP, to which they are assigned that day, *ad lib* after the 8-hour timepoint until 10 pm.

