In the morning of Day 5, after pre-IP use assessments, the subjects will be administered a single pouch/single cigarette of the IP in the sequence to which they have been randomised. IP will be used for 30 minutes with standard use instructions. The cigarette will be smoked in approximately 5 minutes with puffs taken at regular intervals approximately 30 seconds apart. PK sampling will be done pre-IP use and at 2, 5, 7, 15, 20, 30, 45, 60, 90 minutes, 2, 4, 6 and 8 hours post-IP use start. Sampling for plasma cotinine levels will be taken pre-IP use and at 4 and 8 hours post-IP use start. Used pouches will be collected for analysis of nicotine extraction. Questionnaires will be administered to the subject at defined intervals throughout the day. Safety will be followed throughout the day. Subjects will leave the research clinic after completing all 8 h-assessments on Day 5.

[figure not shown]
Visit 3 (End-of-Study phone call)

A follow-up telephone call (Visit 3, end-of-study) will be made on Day 7 (± 1) to follow-up on adverse events.

Subjects will participate in the study for up to 35 days, including an up to 28-day screening period.

An overview of the study design is shown in Figure 8.1-1.

Figure 8.1-1 Overview of study design

The schedule of events for the study is shown overall in Table 8.1-1 and detailed for Day 1-5 in Table 8.1-2. Study assessments are described in Section 11.

Table 8.1-1 Overall schedule of events

Visit	Refer to CSP section:	Screening	In-Clinic						End-of-study
		Visit 1	Visit 2						
Assessment		Day -28 to Day -1	Day -1	Day 1	Day 2	Day 3	Day 4	Day 5	Day 7 (+/- 1 day)
Informed Consent	14.3	X							
Inclusion/exclusion criteria	9.4, 9.5	X	X ¹	X ¹					
Demographics	11.2.3	X							
Snus/cigarette habits	11.2.13	X							
Medical/surgical history	11.2.6	X							
HIV, hepatitis B and C	11.2.8	X							
Alcohol test	11.2.11	X	X						
Urine Drug Screen	11.2.10	X	X						
Pregnancy Test (WOCBP only)	11.2.9	X ²	X ²						
Weight/height (Body Mass Index)	11.2.5	X							
Physical Examination	11.2.4	X							
Clinical Laboratory Profile	11.4.7	X	X						X ³
Vital Signs (Blood pressure and pulse)	11.4.8	X	X	X	X	X	X	X	
12-lead ECG	11.4.9	X	X						X
HSI	11.2.14		X						
PES	11.4.3			X	X	X	X	X	
MCEQ	11.4.4			X	X	X	X	X	
PPS	11.4.5								X
Randomisation	9.9			X					
IP use	10.6			X	X	X	X	X	
PK blood sampling	11.3.1			X	X	X	X	X	
Cotinine sampling	11.4.10			X	X	X	X	X	
Nicotine pouch collection	11.4.2			X	X	X	X	X	
Meals ⁴	9.6.1		X	X	X	X	X	X	

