10.6 Treatment administration

In the morning of Day 1 – 5, subjects will be administered a single pouch/single cigarette as randomised. See Table 10.6-1 for instructions for use of each IP.

Following completion of the single use session and after the 8 hour PK sample, the subjects will move into an ad-lib usage period during which time they will continue to use the assigned product and no other nicotine containing products, until 10pm. The number of units of IP used during *ad lib* use will be recorded in the eCRF by the end of each treatment day.

Table 10.6-1 Investigational products – Instructions for use

Investigational product	Instructions for use
A: ZoneX #2, OND (5.8 mg nic)	A pouch of OND is to be placed between upper lip and gum, and kept still there, for 20 minutes. Oral nicotine pouches are not intended to be chewed during the usage. The IPs should not be swallowed (swallowing saliva in IP use is allowed).
B: ZoneX #3, OND (10.1 mg nic)	A pouch of OND is to be placed between upper lip and gum, and kept still there, for 20 minutes. Oral nicotine pouches are not intended to be chewed during the usage. The IPs should not be swallowed (swallowing saliva in IP use is allowed).
C: Skruf snus Fresh Slim White (10.9 mg nic)	A pouch of Skruf is to be placed between upper lip and gum, and kept still there, for 20 minutes. Oral nicotine pouches are not intended to be chewed during the usage. The IPs should not be swallowed (swallowing saliva in IP use is allowed).
D: [REDACTED]	A pouch of [REDACTED] is to be placed between upper lip and gum, and kept still there, for 20 minutes. Oral nicotine pouches are not intended to be chewed during the usage. The IPs should not be swallowed (swallowing saliva in IP use is allowed).
E: Marlboro Gold, conventional cigarette, (0.8 mg nic)	Subjects should puff approximately every 30 seconds (and should prioritise completion of PK and Questionnaires at the 2 min timepoint). Subject should aim to complete within 10 or 11 puffs and within 5 minutes but is allowed to take longer to finish the cigarette if required.

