11.4 Assessments related to secondary endpoints

11.4.1 *Pharmacokinetic sampling and analysis for secondary endpoints*

Refer to Section 11.3.1.

11.4.2 *Nicotine extraction and flavour analysis from pouches*

The individual nicotine pouch given in the morning and the first pouch for *ab lib*-use will be weighed (in grams, with 2 decimals) before administration to the study subjects. The weight of each pouch will be recorded in the eCRF.

Used pouches will be collected after 20 minutes (+/- 1 minute) of use for the determination of residual nicotine in the IPs (morning pouch) and flavour analysis (*ad lib*-pouch). After the 20-minute exposure period, each pouch will be collected into a labelled poly bag, sealed and frozen. The label should have study number, day number, subject ID and product ID.

All the collected pouches will be frozen immediately at -20°C. Pouches for extraction of nicotine and flavour analysis will be analysed by Reemtsma Labs, Hamburg.

11.4.3 *Products evaluation scale*

The subject will self-assess their experience of product effect using the PES at timepoints detailed in Table 8.1-2.

The rating for each question will be done using a 100 mm VAS scale with the anchor points 0 mm (= Not at all/no urge) and 100 mm (= extremely/extreme urge) printed on paper.

The self-assessment for each question at each time point (in mm's) will be entered in the eCRF by the study personnel.

11.4.4 *Modified cigarette evaluation questionnaire*

The subject will self-assess their experience of cigarette product effect using the MCEQ (12 sub-questions) at timepoints detailed in Table 8.1-2. This questionnaire will only be administered after use of the cigarette product.

Each sub-question about how the study product made the subject feel will be assessed on paper on a 7-grade scale (1- not at all, 2- very little, 3-a little, 4-moderately, 5-a lot, 6- quite a lot, 7-extremely).

The score for each sub-question at each time point will be entered in the eCRF by the study personnel.

11.4.5 *Products preference scale*

The subject will self-assess their product preference using the PPS (2 sub-questions) at timepoints detailed in Table 8.1-2.

The sub-questions: "Please rate the 3 pouch products in order of preference." and "Please rate your use of a cigarette vs use of pouch." (1- prefer cigarette, 2- no preference, 3-prefer pouch) will be assessed at the end of Day 5.

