17.6 Analysis of secondary endpoints

17.6.1 *Pharmacokinetics*

Refer to section 17.5.1.

17.6.2 *In vivo extracted amount of nicotine*

The data needed for the analysis of in vivo extracted amount of nicotine are the individual data of amount of nicotine for unused reference pouches and the amount of nicotine left in the study pouches. The mean nicotine concentration of the reference pouch and weight of each individual study pouch and residual nicotine amount will be used to calculate the extracted amount. The mean of extracted amount (mg/unit) and extraction fraction (%) of nicotine for each IP pouch, will be calculated. The extracted dose of nicotine will be analysed using the signed Wilcoxon rank sum test for within subject difference (i.e. between IPs). Amount of

nicotine in reference pouches and in used pouches will be presented through descriptive statistics.

17.6.3 *Products evaluation scale*

Each sub-question, sub-category and the total score of Questions 1a-g (sub-category 1), 2a-j (sub-category 2), 3a-y (sub-category 3) and 4a will be presented using descriptive statistics at selected timepoints by product including a graph of the mean at each time point.

The total score of PES and the sub-categories will be calculated for each product and intraindividual difference for each timepoint assessed will be analysed using a Wilcoxon Signed Rank Sum test.

17.6.4 *Modified cigarette evaluation questionnaire*

Frequency (number and percentage) for each sub-question will be presented using tables.

17.6.5 *Products preference scale*

The sub-questions 1 will be presented using a frequency table with number of observations and all combinations of the subject's preference.

The sub-question 2 will be presented using a frequency table with number of observations and percent.

No statistical testing will be performed on sub-questions.

17.6.6 *Adverse events*

An overview of all AEs, including SAEs, intensity, relationship to IP, and deaths will be presented by SOC and PT.

Incidence of AEs and SAEs will be summarised by SOC and PT by sequence and overall.

All AE data will be listed by subject and include the verbatim term entered by the Investigator.

17.6.7 *Clinical laboratory analyses*

Clinical laboratory data will be summarised overall with absolute and percent change from baseline.

Abnormal, clinically significant values will be summarised separately, if considered appropriate.

All data will be listed by subject.

17.6.8 *Vital signs*

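### Section 8.1 gives 30 minutes of pouch use on Day 5; every other statement in the protocol gives 20, and 20 should stand.

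*Protocol*

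**What the plan says.** The Day 5 paragraph of protocol Section 8.1 reads "IP will be used for 30 minutes with standard use instructions". The matching Day 5 paragraph in the synopsis reads "IP will be used for 20 minutes with standard use instructions".

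The other statements of use time agree with the synopsis:

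- Synopsis, duration of IP use: "Single 20-minute use of each of the 4 oral nicotine products or a single cigarette use".
- Section 8.1, Day 1: "Oral nicotine IP will be used for 20 minutes with standard use instructions". The paragraphs for Days 2 to 4 also give 20 minutes.
- Section 10.6 covers all five days ("In the morning of Day 1 – 5, subjects will be administered a single pouch/single cigarette as randomised"), and Table 10.6-1 says of each of the four pouches that it is to be "kept still there, for 20 minutes".
- Section 11.4.2: "Used pouches will be collected after 20 minutes (+/- 1 minute) of use".

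Nothing in the protocol explains a longer use on Day 5.

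**The concern.** Time in the mouth is the controlled dosing duration of this relative bioavailability study, and C_max, AUC_t and extracted nicotine all depend on it. Section 8.1 is the main design section, and Day 5 is a full PK day with pouch collection.

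A longer use on Day 5 would not affect all products alike. Four of the five sequences end with a pouch and one ends with the cigarette, so the extra 10 minutes would go to pouches only. The primary model in Section 17.5.1 has fixed effects for period, sequence and product, with no product-by-period term. The period effect therefore cannot absorb the shift, and it would enter the pouch-versus-cigarette contrasts. The extraction analysis in Section 17.6.2 ("The extracted dose of nicotine will be analysed using the signed Wilcoxon rank sum test for within subject difference") makes no period adjustment at all.

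**Working it through.** **Which figure governs.** Table 8.1-1 refers IP use to Section 10.6 and pouch collection to Section 11.4.2. Both give 20 minutes, and neither makes an exception for Day 5. The upper collection limit is 20 + 1 = 21 minutes, so a 30-minute pouch exceeds it by 30 − 21 = 9 minutes. Relative to the intended use it is 30/20 = 1.5 times as long. The other mentions of 30 minutes (a PK time point, a PES question, the eating and drinking restriction) are not use times.

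**Who would be affected.** The Day 5 products under the sequences in Section 9.9 are: sequence 1, E (cigarette); 2, A; 3, B; 4, C; 5, D. Section 9.9 states no allocation ratio. If the 24 subjects are split as evenly as possible (5, 5, 5, 5, 4; an assumption), 24 − 5 = 19 or 24 − 4 = 20 of them use a pouch on Day 5.

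**Effect on the primary ratios.** Let g be the factor by which 30 rather than 20 minutes multiplies exposure, taken as common to all pouches. The protocol gives no value, so I use 1.10 to 1.50. The upper end corresponds to exposure proportional to time, a ceiling if release does not speed up. With equal sequence sizes, product is orthogonal to period and sequence. Each pouch has one fifth of its observations shifted by log g, and the cigarette has none:

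bias in log ratio = (log g)/5 − 0, so the ratio is multiplied by g^(1/5).

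For 24 subjects I fitted the planned model (product, period and sequence, with a common within-subject correlation), placing a shift of log g on pouches in period 5. The four-subject sequence was varied over all five positions. Correlations from 0.3 to 0.9 gave the same result.

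| g | Equal sequences, g^(1/5) | 24 subjects, pouch/cigarette |
|---|---|---|
| 1.10 | 1.019 | 1.017 to 1.020 |
| 1.25 | 1.046 | 1.040 to 1.048 |
| 1.50 | 1.084 | 1.073 to 1.088 |

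Pouch-versus-pouch ratios are unaffected with equal sequences. With 24 subjects and g = 1.50, the largest distortion is a factor of 1.004 in the planned model, and 1.017 in the fallback model without period and sequence.

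**Effect on extraction.** For any pair of pouches, the subjects with one of the two on Day 5 number 5 + 5 = 10 or 5 + 4 = 9 of 24. Those differences would compare 30 minutes with 20. If g also applies to the extracted amount, each pouch's mean is overstated by (g − 1) × 4/24 to (g − 1) × 5/24. That is 1.7% to 2.1% at g = 1.10 and 8.3% to 10.4% at g = 1.50.

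**The case against.** The strongest reply is that this is a one-digit slip with an obvious resolution. The operative sections say 20 and cover Day 5, and use is supervised at a single clinic that will already have run 20 minutes on four days. Pouch collection also stands first in the timing priority order of Section 11.1. A 30-minute use is therefore unlikely in practice. That is correct, and it makes the harm conditional. It does not remove the contradiction from the main design section.

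Section 17.3 already provides for deviations: violations are classified before database lock, and individual PK values may be excluded as the SAP specifies. That also stands. A 30-minute pouch could be handled under those rules, provided it is recognised as a deviation, which the present Section 8.1 text obscures.

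On extraction, the mismatched pairs run in both directions. For A versus B, sequence 2 lengthens A and sequence 3 lengthens B, in about equal numbers. The shifts largely cancel in the paired test and mainly add noise; the overstated means remain.

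Finally, the gain is assumed, one value is used for every endpoint, and the plan reports ratios with 95% confidence intervals and no acceptance margin. The figures show scale only and predict nothing.

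**Conclusion.** The Day 5 use time in Section 8.1 is wrong as written, and 20 minutes is the intended figure. That conclusion rests on the text alone and needs no assumption.

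The size of the consequence is conditional on staff following the Day 5 sentence. If all Day 5 pouches were used for 30 minutes, and that raised exposure by 10% to 50% alike for every pouch, the four pouch-versus-cigarette ratios would be inflated by about 2% to 9%. Pouch-versus-pouch ratios would be nearly unaffected. Mean extracted amounts would be overstated by about 2% to 10%. These figures also assume a near-even split across sequences. It should be corrected because it concerns the dosing duration behind the primary endpoints.

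**What to change.** In the Day 5 paragraph of Section 8.1, replace 30 minutes with 20 minutes, and notify the site.

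If any Day 5 pouch was in fact used for 30 minutes, record it as a protocol deviation against the 20 ± 1 minute rule. Then repeat the C_max, AUC_t and extraction analyses without those observations as a sensitivity check.

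The cost is one number in the protocol and a notice to a single clinic. Design, sampling and the planned model stay as they are.

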8.2 Rationale for study design

The study will provide important safety and PK data to support the design of further studies. The time points for PK blood sampling were selected based on data obtained from previous non-clinical and clinical studies.

A crossover design was chosen to yield a more efficient comparison of treatments than a parallel study design, i.e., fewer subjects are required since each subject will serve as its own control.

A traditional snus with a nicotine strength similar to that of the investigational product was chosen as a comparator to achieve the best possible intra-subject comparison to OND products.

The purpose of the cigarette comparator is twofold; first for Imperial to begin to understand more deeply the potential harm reduction potential of next generation products, such as OND; and also to evaluate the total nicotine exposure of OND against a cigarette, in this case in a single use situation and to inform on future studies in an ad-lib usage situation.

Randomisation will be used to minimise bias in the assignment of subjects to a treatment sequence and to increase the likelihood that known and unknown subject attributes (e.g., demographic and baseline characteristics) are evenly balanced across treatment groups.

9 STUDY POPULATION

Prospective approval of protocol deviations to eligibility criteria, also known as protocol waivers or exemptions, is not permitted.

9.1 Recruitment

The subjects will be recruited from CTC's database of healthy volunteers and from advertising in media (including social media).

9.2 Screening and enrolment log

Investigators must keep a record of all screened subjects even if they were not subsequently included in the study. This information is necessary to verify that subjects were selected without bias. The reason for screen failure should be stated for all subjects screened but not included. The reason for withdrawal should be stated for all subjects included but not completed.

A screening number will be allocated to each subject in connection to the informed consent process at the Screening visit. The screening number is generated automatically in the electronic case report Form (eCRF). The screening number will allow identification of subjects irrespective of their possible eligibility for the study.

Subjects included and randomised will be assigned a randomisation number (101, 102 etc.). If a subject cannot perform the first planned use of IP within 28 days after screening (*i.e.*, the time interval between signing informed consent until first IP use) the subject should be rescreened before proceeding in the study.

9.3 Number of subjects

Twenty Four subjects will be included in the study. Approximately 48 subjects will be screened to achieve a total of 24 randomised subjects.

For replacements of subjects who discontinue from the study, see Section 9.8.

9.4 Inclusion criteria

For inclusion in the study, subjects must fulfil the following criteria:

1. Willing and able to give written informed consent for participation in the study.
2. Male or female subject aged ≥ 19 years at the time of screening.
3. Body Mass Index (BMI) ≥ 18.0 and ≤ 30.0 kg/m².
4. Clinically normal medical history, physical findings, vital signs, ECG and laboratory values at the time of screening, as judged by the Investigator.
5. Dual user of snus and conventional cigarettes for ≥ 1 year, with a minimum weekly consumption of two or more snus cans and >5 cigarettes, and who is willing and able to use brands with nicotine content $\geq 1\%$.

